**Table 2 Maintenance Treatment for the *Follicular Lymphoma* Dose-Escalation Phase**

Patient Population	Regimen
Patients with FL	
Maintenance treatment consisting of the following, administered for approximately 24 months (from Months 1–24):
 
 
• Lenalidomide 10 mg PO once daily on Days 1–21 of each month for a maximum of 12 months
 
• Obinutuzumab 1000 mg IV on Day 1 of every other month (i.e., every 2 months) for a maximum of 24 months
 

FL=follicular lymphoma; IV=intravenous; PO=by mouth.

[figure not shown]
Notes: A month is defined as 28 days. Treatments will be administered sequentially in the following order: lenalidomide followed by obinutuzumab.

### 3.1.2.1.3 Dose-Escalation Rules

A standard 3+3 dose-escalation schema will be used. The obinutuzumab dose will remain fixed at 1000 mg during the dose-escalation phase. The starting doses in Cohort 1 are 1.4 mg/kg for polatuzumab vedotin and 10 mg for lenalidomide. In Cohorts 2–6, dose escalation of polatuzumab vedotin and lenalidomide will proceed in

increments that parallel the magnitude of dose increases tested in ongoing Phase Ib studies (see Sections 3.3.3.2 and 3.3.3.2.2). For polatuzumab vedotin, there are two possible dose levels: 1.4 or 1.8 mg/kg. For lenalidomide, there are three possible dose levels (10, 15, or 20 mg). Inpatient dose escalation is not allowed. The *FL* dose-escalation plan is depicted in Figure 2, and the doses for each cohort are summarized in Table 3.

**Figure 2 Follicular Lymphoma Dose-Escalation Plan**

If Cohort 1 doses are deemed safe and tolerable, escalation will continue with simultaneous enrollment of Cohort 2 (only the polatuzumab vedotin dose will increase) and Cohort 3 (only the lenalidomide dose will increase).

Escalation to Cohort 4 may occur only if Cohort 2 doses and Cohort 3 doses are deemed safe and tolerable.

If Cohort 4 doses are not tolerable, escalation may continue with Cohort 5 (based on tolerated Cohort 3 dose combination, in which only the lenalidomide dose will increase).

If the Cohort 4 doses are safe and tolerable, further escalation will occur with enrollment of Cohort 6 (only the lenalidomide dose will increase).

**Table 3 Follicular Lymphoma Dose-Escalation Cohorts**

Cohort	Obinutuzumab a	Polatuzumab Vedotin b	Lenalidomide c
1	1000 mg	1.4 mg/kg	10 mg
2	1000 mg	1.8 mg/kg	10 mg
3	1000 mg	1.4 mg/kg	15 mg
4	1000 mg	1.8 mg/kg	15 mg
5	1000 mg	1.4 mg/kg	20 mg
6	1000 mg	1.8 mg/kg	20 mg

a Obinutuzumab will be administered intravenously at a fixed dose of 1000 mg. During Cycle 1, obinutuzumab will be administered on Days 1, 8, and 15. During Cycles 2–6, obinutuzumab will be administered on Day 1 only.

b Polatuzumab vedotin will be administered intravenously on Day 1 of each 28-day cycle.

c Lenalidomide will be administered orally on Days 1–21 of each 28-day cycle.

Dose escalation will occur in accordance with the rules listed below.

- A minimum of 3 patients will initially be enrolled in each cohort. *The first 3 patients in each cohort will be sequentially enrolled and dosed at least 48 hours apart.*
- If none of the first 3 DLT-evaluable patients experiences a DLT, the doses in that cohort will be deemed safe and tolerable and escalation may continue per the dose-escalation plan described above.
- If 1 of the first 3 DLT-evaluable patients experiences a DLT, the cohort will be expanded to 6 patients. If there are no further DLTs in the first 6 DLT-evaluable patients, the doses in that cohort will be deemed safe and tolerable and escalation may continue per the dose-escalation plan described above.
- If a DLT is observed in  $\geq 33\%$  of patients (e.g., 2 or more of up to 6 DLT-evaluable patients), the dose combination at which this occurs will be considered intolerable and the MTD will have been exceeded for polatuzumab vedotin and/or lenalidomide in the G+Pola+Len treatment combination. However, enrollment may continue in alternative cohorts according to the dose-escalation plan described above.
- If the MTD is exceeded in any cohort, the highest dose combination at which  $< 33\%$  of patients (e.g., 2 of 6 DLT-evaluable patients) experience a DLT will be declared the combination MTD (i.e., the MTDs for polatuzumab vedotin and lenalidomide in the G+Pola+Len treatment combination).
- If the MTD is not exceeded at any dose level, the highest dose combination administered in this study will be declared the maximum administered dose for polatuzumab vedotin and lenalidomide in the G+Pola+Len treatment combination.

If the MTD is exceeded in any cohort, de-escalation of the polatuzumab vedotin dose and/or the lenalidomide dose and adjustment of treatment schedules (e.g., lenalidomide treatment on Days 1–10) may occur. It is possible that more than one combination MTD (i.e., potential RP2Ds) will be identified, which may consist of different dose or schedule

combinations for polatuzumab vedotin and lenalidomide that are deemed safe and tolerable when combined with a fixed dose of obinutuzumab. If this occurs, it is possible that more than one expansion cohort will be enrolled to gather additional safety, PK, and PD data at these RP2Ds and schedules. Additional patients may be enrolled in a given cohort in the absence of DLTs to acquire additional safety data for the appropriate dose levels in the expansion phase of the study.

On the basis of a review of real-time safety data and available preliminary PK data, dose escalation may be halted or modified by the Sponsor as deemed appropriate.

Relevant demographic, adverse event, laboratory, dose administration/intensity, and PK (if available) data will be reviewed *throughout the study by the Clinical Study Team and prior to dose-escalation decisions, which will be made by the Medical Monitor in consultation with the Principal Investigator and participating investigators.*

Although the DLT assessment window is defined as the first treatment cycle, cumulative or late toxicities occurring beyond the first cycle may be considered when determining the RP2Ds. *Prior to opening the R/R FL expansion phase, the Clinical Study Team and the Medical Monitor will review the cumulative data, recommend the RP2D, and review this with the IMC for approval.*

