## 6.1 DETERMINATION OF SAMPLE SIZE

Limited dose finding will be conducted during the dose-escalation phase of this study. The estimated sample size follows from the dose-escalation rules for a standard 3+3 algorithm, as outlined in Section 3.1. It is anticipated that enrollment of 5 cohorts of 3–6 patients each, for a total of 18–30 patients, will be required to establish the RP2D during the dose-escalation phase *for patients with R/R FL. An additional 3 possible cohorts of 3–6 patients each, for a total of 12–18 patients will be required to establish the RP2D during the dose-escalation phase for patients with R/R DLBCL.*

Approximately 80 patients (40 patients with FL and 40 patients with DLBCL) will be enrolled during the expansion phase. Overall, approximately 110–128 patients will be enrolled in the study.

The primary efficacy analysis will be the estimation of the true proportion of patients expected to obtain a PET-CT–defined CR at EOI.

Data from completed and ongoing studies in similar disease settings will be used as historical controls for comparison. Currently available data indicate that the historical CR rate based on PET-CT scans is 40% for R/R FL and DLBCL.

A sample size of 40 patients is deemed sufficient to provide adequate precision for the point estimate and for the lower bound of the two-sided 90% CI to rule out a clinically uninteresting probability of response of <55%, assuming an observed PET-CT–defined CR rate of 70%.

Table 22 lists the two-sided 90% Clopper-Pearson exact CIs for the true probability of achieving a PET-CT–defined CR at EOI for a range of observed proportions based on a sample of 40 patients.

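### The written 3+3 rules let a dose be declared the MTD or maximum administered dose on 0 DLTs in 3 patients, and the minimum enrolments in Section 6.1 do not follow from those rules

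*Combined protocol and SAP*

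**What the plan says.** The escalation bullets are the same in Section 3.1.2.1.3 (FL, after Table 3) and in the Dose-Escalation Rules of Section 3.1.3.1 (DLBCL, after Table 8). There are two ways to pass:

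- No DLT in three: "If none of the first 3 DLT-evaluable patients experiences a DLT, the doses in that cohort will be deemed safe and tolerable".
- One DLT in three: "If 1 of the first 3 DLT-evaluable patients experiences a DLT, the cohort will be expanded to 6 patients", and then "If there are no further DLTs in the first 6 DLT-evaluable patients, the doses in that cohort will be deemed safe and tolerable".

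Two further bullets make the final declaration. If some cohort exceeds the MTD, the highest combination with fewer than 33% DLTs is the combination MTD. If none does, "the highest dose combination administered in this study will be declared the maximum administered dose". Neither bullet says how many evaluable patients must have been treated at that dose. The text after the bullets adds "Additional patients may be enrolled in a given cohort in the absence of DLTs", which is permission and not a requirement.

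Section 6.1 says the estimated sample size follows from the 3+3 rules. It anticipates 18–30 patients for five FL cohorts of 3–6 and, for DLBCL, "3 possible cohorts of 3–6 patients each, for a total of 12–18 patients". With 80 expansion patients, the overall total is 110–128.

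**The concern.** Moving up a dose on 0 of 3 is ordinary 3+3 practice. Here the same 0 of 3 also suffices for the final declaration, in two situations: the next cohort fails, or the top cohort shows no DLT in three. The written rules then stop with three evaluable patients at the declared dose.

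Section 2.1 bases the RP2D on the incidence of first-cycle DLTs, and about 40 further patients per histology are treated at it. Section 6.10 mentions possible analyses for stopping on safety grounds but gives no numerical boundary. The number of evaluable patients behind the declaration therefore matters, and the rules and the sample-size section give different impressions of what it is.

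**Working it through.** **1. The plan's own totals.** Inputs are the cohort counts and sizes in Section 6.1.

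| | Cohorts × 3 | Cohorts × 6 | Stated |
|---|---|---|---|
| FL, 5 cohorts | 15 | 30 | 18–30 |
| DLBCL, 3 cohorts | 9 | 18 | 12–18 |
| Overall, adding 80 | 104 | 128 | 110–128 |

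The upper ends reproduce. Each lower end is 3 too high, and the overall minimum is 6 too high (80 + 18 + 12 = 110; 80 + 15 + 9 = 104). Both minima are matched by one cohort of six: 4×3 + 6 = 18 and 2×3 + 6 = 12. The FL figure is also 6×3 = 18. Table 3 lists six cohorts, although under Figure 2 Cohorts 5 and 6 are alternatives.

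**2. Chance that a dose passes.** With true DLT rate p:

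- 0 of 3: (1−p)³
- 1 of 3, then none in the next three: 3p(1−p)² × (1−p)³
- for comparison, at most 1 of 6: (1−p)⁶ + 6p(1−p)⁵

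At p = 1/3 the first route gives (2/3)³ = 29.6%. The second gives 0.4444 × 0.2963 = 13.2%. The written rule therefore passes 42.8%. At most 1 of 6 gives 8.8% + 26.3% = 35.1%.

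| True DLT rate | 0/3 alone | Full written rule | At most 1 of 6 |
|---|---|---|---|
| 20% | 51.2% | 70.9% | 65.5% |
| 33.3% | 29.6% | 42.8% | 35.1% |
| 40% | 21.6% | 30.9% | 23.3% |
| 50% | 12.5% | 17.2% | 10.9% |

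At 1/3, 29.6/42.8 = 69% of passes come from 0 of 3.

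**3. Exact one-sided 95% upper bounds on the DLT rate.**

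- 0/3: 1 − 0.05^(1/3) = 63%
- 0/6: 1 − 0.05^(1/6) = 39%
- 1/6: the p solving (1−p)⁶ + 6p(1−p)⁵ = 0.05, which is 58%

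**4. How often the declaration rests on three patients (DLBCL, Cohorts A–C).** The documents give no DLT rates for the triplet, so these are assumptions. With rates of 10/25/40%, the full-rule pass probabilities are 0.906, 0.600 and 0.309, and the 0/3 probabilities are 0.729, 0.422 and 0.216.

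- A declared on 0/3, B fails: 0.729 × 0.400 = 0.292
- A passes, B declared on 0/3, C fails: 0.906 × 0.422 × 0.691 = 0.264
- A and B pass, C declared on 0/3: 0.906 × 0.600 × 0.216 = 0.117

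The sum is 67%. The same calculation gives 73% with 5/15/30% and 59% with 15/33/50%. In the 10/25/40% case, the 40% dose is declared with probability 0.906 × 0.600 × 0.309 = 17%. Requiring at most 1 of 6 at that dose gives 0.906 × 0.600 × 0.233 = 13%.

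**5. The 2-of-6 example.** One bullet treats 2 of 6 as past the limit: "e.g., 2 or more of up to 6 DLT-evaluable patients), the dose combination at which this occurs will be considered intolerable". The next offers it as an example of fewer than 33%: "e.g., 2 of 6 DLT-evaluable patients) experience a DLT will be declared the combination MTD". Two of six is 33.3%, so it cannot illustrate both.

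**The case against.** The strongest reply is that this is a limitation of any 3+3 design and that the protocol does not stop at the bullets. Cumulative and late toxicity may be considered. The study team's review goes to the IMC for approval before expansion opens. Extra patients can be added at a DLT-free dose for exactly this purpose. Section 3.1.4 has the IMC reviewing cumulative data at regular intervals, with power to recommend holding enrolment. All of this stands, so a declared MTD is not automatically the expansion dose; Section 3.1.2.1.3 itself calls combination MTDs potential RP2Ds. However, the review and approval steps do not add evaluable patients, and the step that would is optional.

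A second reply is that six patients would change little: 43% falls to 35% at a rate of 1/3, and a 1/6 result still has a 58% upper bound. That is also fair. Most of the 43% belongs to the 3+3 design, not to stopping at three.

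A reader might infer more than the documents support:

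- **That passing on 0 of 3 carries a 43% risk at the 33% limit.** It carries 30%. The other 13 points are passes at 1/6, which already use six patients.
- **That Section 6.1 requires a 6-patient cohort.** Its totals are anticipated. The FL 18 may be left over from a six-cohort plan, since the amendment summary shows the earlier six-cohort wording removed. Replacement of non-evaluable patients could also account for the extra three in either group.
- **That RP2D determination is a primary objective.** Section 2.1 lists it under safety objectives without that label.

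**Conclusion.** The point holds as a mismatch between the escalation rules and the sample size said to follow from them. As written, 0 DLTs in 3 evaluable patients is enough to declare the MTD or maximum administered dose in either histology, while the stated minima are each 3 patients above what those rules need when every counted cohort is opened.

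The statistical cost is moderate. At a true DLT rate of 1/3, the written rule passes 43% against 35% for at most 1 of 6. The clearer gain is in precision when no DLT is seen: a 39% upper bound with six patients against 63% with three. These figures assume independent patients with a common DLT rate. The 59–73% share of trials declaring on three patients, and the 17% and 13% figures, depend also on the assumed dose–toxicity curves and on no optional patients being added.

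The plan should be clarified before the expansion dose is chosen. The documents do not show that an unsafe dose would reach expansion unchecked.

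**What to change.** Reconcile the declaration bullets in Sections 3.1.2.1.3 and 3.1.3.1 with Section 6.1, in one of two ways:

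1. State in the bullets the minimum number of DLT-evaluable patients at the declared dose that the 12 and 18 minima imply, namely six, and leave 0 of 3 as the rule for escalating. The cost is usually 3 more patients per histology than the literal rules need, generally within the stated ranges, and one more Cycle 1 window before expansion. Patients treated at the RP2D also count in the pooled efficacy analysis of Section 6.6.
2. Keep the rules and restate the minima as 15 (FL) and 9 (DLBCL), with 104–128 overall, there and wherever the totals are repeated (synopsis, Sections 3.1.1, 3.1.2.1 and 3.1.3.1). This costs wording only, but accepts that the declaration may rest on three patients.

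In either case, report the DLT rate at the selected RP2D with its number of evaluable patients and its exact one-sided 95% upper bound, so that the IMC sees how much the escalation data exclude. In the same edit, reconcile the two uses of 2 of 6. Which side of the limit it falls on is for the sponsor to decide.

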### Dose-Escalation Rules

A standard 3 +3 dose-escalation schema will be used. The rituximab and polatuzumab dose levels will remain fixed during the dose-escalation phase, and only the lenalidomide will be dose escalated. The polatuzumab dose of 1.8 mg/kg is based on ongoing Phase II trials (see Sections 1.3.2 and 3.3.3.3). Inpatient dose escalation is not allowed. The overall DLBCL dose-escalation plan is depicted in [Figure 3](#).

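### The MTD-declaration rule gives 2 of 6 as its example of fewer than 33% with a DLT, but 2/6 is 33.3% and the bullet before it calls that count intolerable

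*Combined protocol and SAP*

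**What the plan says.** Both histologies use the same algorithm. The FL section states "A standard 3+3 dose-escalation schema will be used" and the DLBCL section states "A standard 3 +3 dose-escalation schema will be used". The bullets below Table 3 (FL) and Table 8 (DLBCL) then set these rules:

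- **Tolerable after expansion.** If 1 of the first 3 evaluable patients has a DLT, the cohort grows to 6. "If there are no further DLTs in the first 6 DLT-evaluable patients, the doses in that cohort will be deemed safe and tolerable".
- **Intolerable.** The criterion is a DLT rate of at least 33%, illustrated as follows: "e.g., 2 or more of up to 6 DLT-evaluable patients), the dose combination at which this occurs will be considered intolerable". Such a dose counts as above the MTD.
- **MTD declaration.** This rule opens "If the MTD is exceeded in any cohort, the highest dose combination at which" and sets its cut-off at <33%. Its example and outcome then read: "of patients (e.g., 2 of 6 DLT-evaluable patients) experience a DLT will be declared the combination MTD".

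The text after the bullets, in both sections, also permits larger cohorts: "Additional patients may be enrolled in a given cohort in the absence of DLTs to acquire additional safety data". Before the FL expansion opens, the study team and Medical Monitor "recommend the RP2D, and review this with the IMC for approval". The DLBCL section has an equivalent step.

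**The concern.** The second and third rules stand next to each other and use the same count for opposite outcomes. Two DLTs in six patients illustrates a dose above the MTD in one bullet and the MTD itself in the next. The third rule applies only once some cohort has exceeded the MTD, so a 2-of-6 cohort would both trigger that rule and match its example of the dose to be declared.

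An example in a decision rule is there to settle the boundary case, and here it settles it the wrong way. Someone checking a 2-of-6 cohort finds printed support for both answers. If the example were followed instead of the threshold, a dose the protocol classes as intolerable would be declared the combination MTD. In the FL section a combination MTD is expressly a candidate RP2D, and about 40 FL patients are then treated at the RP2D. The DLBCL section does not use that phrase, but its dose escalation likewise leads to an RP2D given to about 40 patients.

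**Working it through.** **Step 1. Check the example against the threshold.** The inputs are the counts and cut-offs in the bullets of Sections 3.1.2.1.3 and 3.1.3.1.

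| DLTs of 6 | Proportion | <33%? | <1/3? | Intolerable under the ≥33% bullet? |
|---|---|---|---|---|
| 1 | 1/6 = 16.7% | yes | yes | no |
| 2 | 2/6 = 33.3% | no | no | yes |
| 3 | 3/6 = 50.0% | no | no | yes |

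The printed example cannot be reproduced: 2 of 6 does not satisfy <33%. Reading the symbol as ≤33% does not rescue it, because 33.3% still exceeds 33% and the preceding bullet still calls 2 of 6 intolerable. With six evaluable patients, 1 is the largest DLT count below the threshold.

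**Step 2. Check it against the expansion rule.** A cohort with 1 DLT in the first 3 is tolerable only if no more occur among the 6, so the largest tolerable count on that path is 1 of 6. This agrees with Step 1.

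**Step 3. How often would a cohort land on 2 of 6?** The documents give no DLT rate, so the true rate *p* is assumed.

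- Path A, the written rule: 1 DLT in the first 3, then 1 in the next 3. Probability [3p(1−p)²]² = 9p²(1−p)⁴.
- Path B, optional enlargement: 0 DLTs in the first 3, cohort enlarged to six, then 2 in the next 3. Probability (1−p)³ × 3p²(1−p) = 3p²(1−p)⁴. This assumes that every such cohort is enlarged, and to exactly six. The protocol permits additional patients but gives no number.
- Upper total: 12p²(1−p)⁴.

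| Assumed *p* | Path A | Path B | Upper total |
|---|---|---|---|
| 10% | 9 × 0.01 × 0.6561 = 5.9% | 2.0% | 7.9% |
| 20% | 9 × 0.04 × 0.4096 = 14.7% | 4.9% | 19.7% |
| 30% | 9 × 0.09 × 0.2401 = 19.4% | 6.5% | 25.9% |
| 40% | 9 × 0.16 × 0.1296 = 18.7% | 6.2% | 24.9% |

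**Step 4. What if the example were followed?** Without optional enlargement, a cohort qualifies with probability (1−p)³ + 3p(1−p)⁵. Accepting 2 of 6 adds 9p²(1−p)⁴.

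- p = 33%: 0.434 rises to 0.632, a ratio of 0.632/0.434 = 1.46.
- p = 40%: 0.309 rises to 0.496, a ratio of 0.496/0.309 = 1.61.

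These hold only if staff let the example override the stated threshold.

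**The case against.** The strongest reply is that the example does not govern. The operative criterion is <33%, and a parenthetical illustration does not amend it. Applied as written, the criterion rejects 2 of 6, the ≥33% bullet calls it intolerable, and the expansion bullet allows at most 1 of 6. The FL section also describes candidate RP2Ds as combinations judged safe and tolerable, which a 2-of-6 cohort is not. Escalation decisions rest with the Medical Monitor in consultation with the investigators, and the RP2D goes to the IMC for approval before each expansion opens.

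All of that stands, and it is why the practical risk is small. It shows which reading is intended, but it does not make the printed example right.

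The reply also holds that the probabilities add little, because they rest on assumed rates and, for the upper totals, on assumed enlargement. That is fair. They show that the boundary count is an ordinary outcome of the algorithm, and nothing more should be drawn from them.

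**Conclusion.** The concern holds. In both the FL and the DLBCL rules, the example in the MTD-declaration bullet contradicts its own threshold and the preceding bullet, on any reading of the inequality sign. This conclusion rests only on the protocol's text and on 2/6 = 33.3%, with no assumption.

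The size is minor. The error is confined to one illustrative count printed in two places, and the surrounding rules and the approval step all point the right way. At assumed true DLT rates of 10% to 40%, roughly 6% to 19% of cohorts would reach 2 of 6 by the written path, and up to about 26% if every cohort with no DLT in the first three were enlarged to six. These describe how often the misprinted count would arise. They are not the chance of a wrong MTD or RP2D.

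**What to change.** In the MTD-declaration bullet of Section 3.1.2.1.3 and again in Section 3.1.3.1, replace 2 of 6 with 1 of 6. This is the boundary count that satisfies the <33% threshold, the ≥33% bullet and the expansion bullet together. An amendment or a clarification letter would do. The cost is one number changed in two places, with no extra patients and no change to the design.

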### **3.1.2.2 Follicular Lymphoma Expansion Phase**

The expansion phase is designed to further assess the safety and efficacy of polatuzumab vedotin and lenalidomide at their respective RP2Ds when combined with a fixed dose of obinutuzumab *in FL patients.*

Approximately 40 patients with FL will be enrolled during the expansion phase and treated as described below.

All patients enrolled in the expansion phase will receive induction treatment as outlined in [Table 4](#). When study treatments are given on the same day, they will be administered sequentially in the following order: lenalidomide, obinutuzumab, and polatuzumab vedotin.

